
Statistical Methods:
	
Primary efficacy analyses will be based upon an intent-to-treat (ITT) philosophy. The primary efficacy population will be the Full Analysis Set (FAS) which will include all randomized subjects who received at least one dose of study drug. Analyses performed on the Per Protocol (PP) population will be considered supportive. Subjects will be analyzed within the treatment group to which they are randomized.
 
Efficacy Analyses:
 
The primary efficacy endpoint is a binary variable taking on values of responder or non-responder. Subjects will be considered a responder if they have at least a 4-point reduction in WI-NRS between baseline and Week 8. Missing data imputation will be used for subjects who fail to complete the eDiary at Week 8. The primary endpoint will be summarized with descriptive statistics by treatment group and study week.
 
The difference in the primary efficacy outcome measure between treatment groups will be tested using a Cochran Mantel Haenszel (CMH) test controlling for the stratification factors. The same test will be used for the Week 4 responder rates. Testing, using an analysis of covariance (ANCOVA) model, of the change in WI-NRS to Day 7 and Day 3 will be employed.

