### 8.1 Decision Rule and Sample Size

The decision rule is based on the Phase 2b screening methodology presented in Fleming and Richardson ([Fleming 2004](#)). The two-category decision guideline as applied to this clinical trial compares the observed one-sided p-value for the primary endpoint to two categories: (0.025, 0.05) and (0, 0.025).

- If the one-sided p-value is between 2.5% and 5% then the serlopitant-based regimen is plausibly efficacious and should be evaluated definitively in a subsequent Phase 3 clinical trial.
- If the one-sided p-value is less than 2.5%, then the serlopitant-based regimen will have met the generally accepted level of evidence required to demonstrate efficacy.

The sample size of 100 per group has been selected to achieve 90% power for the primary endpoint with

- 5% one-sided alpha and responder rates of 24% (placebo) and 43.5% (serlopitant)
- 2.5% one-sided alpha and responder rates of 24% (placebo) and 46% (serlopitant)

Testing of the key secondary endpoints will take place should statistical significance be reached for the primary endpoint. Testing within the key secondary endpoints will be hierarchical with testing starting with the WI-NRS Week 4 responder rate, then the Day 7 WI-NRS endpoint, and finally the Day 3 WI-NRS endpoint.

The sample size calculations have been performed in PASS 13 ([“PASS 13 Power Analysis and Sample Size Software” 2014](#)) and use a Chi-Squared test. The primary analysis will control for the stratification factors. It is expected that this unstratified power estimate will under-estimate the true power as it does not take the variance reduction resulting from stratification into account ([Matts 1988](#)).

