Each complete dataset formed by multiply imputed data will be analyzed as specified for the particular analysis. The results from the analyses will be combined into a single inference using SAS® PROC MIANALYZE. In the case of the primary analysis and the secondary responder analyses, the Cochran Mantel Haenszel (CMH) statistics computed in the analyses of WI-NRS responder rates will be normalized using the Wilson-Hilferty transformation prior to combining them using SAS® PROC MIANALYZE

A total of 2 random seeds will be needed to impute missing data. Those random seeds have been pre-specified by using a random number generator:

- WI-NRS Serlopitant: Seed= 85162995
- WI-NRS Placebo: Seed= 878201528

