#### **8.8 Efficacy Analyses**

The efficacy endpoints will be summarized within the FAS and PP populations using descriptive statistics by time point and treatment. Results including averaged imputed values will be summarized at Baseline, Week 2, 4, 8 and Follow-up and the change from baseline for these measures will be summarized at Week 2, 4, 8 and Follow-up. The WI-NRS

measures will also be summarized at Week 6. The WI-NRS and change from baseline will also be presented for each study day. The PGIC is a measure of change and so will only be summarized at Week 2, 4, 8 and Follow-up.

For the 4 and 3 point responder rate endpoints, subjects will be considered responders if they have at least a 4 / 3 point reduction between baseline and the corresponding week and the subject did not use an excluded medication to treat their pruritus or psoriasis.

The difference in the primary efficacy outcome measure (WI-NRS 4-point responder rate at Week 8) will be tested using a CMH test controlling for the ‘as randomized’ stratification factors. Conceptually the hypotheses being tested are:

$$H_0: P_{Placebo} \geq P_{Serlopitant} \quad H_a: P_{Placebo} < P_{Serlopitant}$$

where  $P_{Placebo}$  is the percent of placebo responders and  $P_{Serlopitant}$  is the similar percent for serlopitant. The primary endpoint will utilize the missing data rules as outlined in [Section 8.2](#).

The remaining key secondary endpoints will be analyzed using an analysis of covariance (ANCOVA) model with treatment group and stratification factor as fixed effects and the respective baseline values as a covariate. Both least squares means and observed means will be presented.

To confirm the assumptions for the ANCOVA model (i.e., that the errors are normally distributed with equal variances), residuals will be examined using the Shapiro-Wilk test. If there is overwhelmingly strong evidence that the assumptions are not satisfied, the data will be rank-transformed prior to submitting to the ANCOVA. Results of the rank-transformed analysis then will be considered the primary analysis; however, results of the non-rank-transformed analysis will also be presented.

The preceding analyses are to be conducted for the FAS and PP populations.

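### Section 8.2 pools an unsigned, Wilson-Hilferty-transformed CMH statistic, and no rule turns the pooled result into the one-sided p-value on which Section 8.1 decides

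*Protocol*

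**What the plan says.** Four parts of the protocol meet here.

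- **Test and hypothesis (Section 8.8).** The primary endpoint, the "WI-NRS 4-point responder rate at Week 8) will be tested using a CMH test controlling for the" as-randomized strata. The alternative is directional: the placebo responder rate is below the serlopitant rate.
- **Decision (Section 8.1).** The rule "compares the observed one-sided p-value for the primary endpoint to two categories", with cut-offs at 0.025 and 0.05. The lower band counts as demonstrating efficacy, the band between as plausible efficacy to be tested in Phase 3. The same result is the gate for what follows: "Testing of the key secondary endpoints will take place should statistical significance be reached for the primary endpoint".
- **Pooling (Section 8.2).** Missing WI-NRS values are imputed 25 times within each arm. "The results from the analyses will be combined into a single inference using SAS® PROC MIANALYZE". For the primary and secondary responder analyses, the CMH "statistics computed in the analyses of WI-NRS responder rates will be normalized using the Wilson-Hilferty transformation prior to combining them".
- **Week 4 (Synopsis, Statistical Methods).** "The same test will be used for the Week 4 responder rates".

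No section says which tail of the pooled value is read, whether it is halved, or how the direction of the difference enters.

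**The concern.** The pooled quantity and the decision quantity are of different kinds. A 1-df CMH chi-square is the square of a z-statistic, so its transform is equally large whether serlopitant or placebo does better. The protocol therefore prescribes a calculation whose direct output is not the p-value its decision rule needs.

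That p-value sets the decision category and opens the key secondary hierarchy. At least three readings of the pooled value are open: its upper tail, a two-sided test of it against zero, or half its upper tail with a direction check. The same data can land in different categories under each. Choosing among them after unblinding is what a fixed decision rule is meant to prevent. A lesser point is that a pooled transformed chi-square gives no pooled treatment difference or confidence interval.

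**Working it through.** **Inputs from the protocol.** 100 per arm; 24% vs 43.5% at one-sided 5%; 24% vs 46% at one-sided 2.5%; stated power 90% from an unstratified chi-squared test (Section 8.1). Allocation 1:1 (Section 5.8.1). 25 imputations (Section 8.2).

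**1. The protocol's own power.** Power = Φ{[(p₂ − p₁) − z_α √(2p̄(1 − p̄)/n)] / √[(p₁q₁ + p₂q₂)/n]}.
- 24% vs 43.5%, α = 0.05: (0.195 − 1.645 × 0.0669)/0.0654 = 1.299, power 90.3%.
- 24% vs 46%, α = 0.025: (0.22 − 1.960 × 0.0675)/0.0656 = 1.338, power 90.9%.

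The stated 90% is reproduced, so the sample size is not in question.

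**2. What the transform does.** For 1 df, W = (X^(1/3) − 7/9)/√(2/9), with X the CMH chi-square.

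| Signed z | X | W | Upper tail of W | Chi-square p | True one-sided p |
|---|---|---|---|---|---|
| 1.645 | 2.706 | 1.306 | 0.096 | 0.100 | 0.050 |
| 1.960 | 3.84 | 1.672 | 0.047 | 0.050 | 0.025 |
| −1.960 | 3.84 | 1.672 | 0.047 | 0.050 | 0.975 |

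The sign is lost and the upper tail follows the two-sided p-value. An upper tail of 0.05 needs \|z\| ≥ 1.936, a true one-sided level of 0.026. An upper tail of 0.025 needs \|z\| ≥ 2.220, a level of 0.013. A two-sided test of W against zero is worse: X = 0, no difference at all, gives W = −1.650 and p = 0.099.

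**3. Worked outcomes.** Complete data, one stratum, 24/100 placebo responders, hypergeometric (N − 1) variance. For 36 serlopitant responders: observed minus expected = 36 − 30 = 6; variance = 100 × 100 × 60 × 140/(200² × 199) = 10.55; z = 1.847; X = 3.411; W = 1.543.

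| Serlopitant responders | One-sided CMH p | Category | Upper tail of W | Category if read directly |
|---|---|---|---|---|
| 35 | 0.044 | plausible | 0.085 | none |
| 36 | 0.032 | plausible | 0.061 | none |
| 37 | 0.023 | demonstrated | 0.044 | plausible |
| 38 | 0.016 | demonstrated | 0.031 | plausible |

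**4. Operating characteristics.** Exact enumeration of all 101 × 101 outcomes, complete data, one stratum.

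| Reading | Power, 24% vs 43.5%, 0.05 | Power, 24% vs 46%, 0.025 | Claims for serlopitant at 24% vs 24% (0.05 / 0.025) |
|---|---|---|---|
| Signed CMH, one-sided | 90.2% | 90.8% | 5.03% / 2.43% |
| Upper tail of W | 84.3% | 85.9% | 2.6% / 1.3% |
| Two-sided test of W | 76.5% | 79.1% | not needed here |
| Half the upper tail, direction checked | 90.8% | 91.3% | 5.3% / 2.6% |

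On the upper-tail reading the category is lowered in 12.8% of trials at 43.5% and 8.6% at 46%. With the rates reversed (46% placebo, 24% serlopitant), the upper tail is below 0.025 in 85.9% of trials, so direction must come from somewhere outside the pooled statistic.

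**5. The pooling step.** Simulation with two strata, 25 within-arm imputations and 3,000 trials per cell. The missing share and a correlation of 0.6 are assumptions; the protocol gives neither.

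| Missing | 0.05 tier: halving rule / pooled signed difference | 0.025 tier: halving rule / pooled signed difference |
|---|---|---|
| 0% | 90.7% / 90.8% | 91.3% / 91.4% |
| 10% | 89.6% / 89.6% | 89.7% / 89.8% |
| 20% | 87.5% / 87.7% | 87.0% / 87.2% |

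Both methods lose the same power to missing data, so that loss is not due to the transform.

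**The case against.** The strongest reply is that Section 8.1 already calls for a one-sided p-value and Section 8.8 already gives the direction. Halving a 1-df chi-square p-value and checking the sign is routine, and the statistical analysis plan, due before unblinding, may say so. Every power loss above then describes a misreading. The pooling simulation also shows no weakness in the transform once it is read correctly.

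Much of this stands. A one-sided p-value can be recovered, the losses are conditional on the reading, and no false-positive risk in favour of serlopitant arises from the upper-tail reading. Preferring a method that also gives an estimate and interval is a secondary argument, since the protocol promises only a test. It is also true that Section 8.1 ties the one-sided p-value to the primary endpoint alone.

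What does not stand is that this was left to the analysis plan. Section 8.2 itself fixes the imputation code, the number of imputations, the seeds, the transform and the combining procedure. Followed literally, that sequence ends in a two-sided-type p-value, and an analysis plan that reproduced it would inherit the gap. Naming a one-sided p-value in Section 8.1 does not say how the pooled value becomes one.

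**Conclusion.** The concern holds and should be fixed. As written, Section 8.2 does not deliver the p-value that Sections 8.1 and 8.8 require. Reading the upper tail directly costs 90.2 − 84.3 = 5.9 points of power at the 0.05 tier and 90.8 − 85.9 = 4.9 points at the 0.025 tier. The likely harm is a missed or downgraded result. A false claim for serlopitant is not the risk. The sample size and its 90% power stand once the rule is stated.

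The exact figures assume complete data, one stratum and the protocol's own responder rates. The simulated figures also rest on assumed missingness and correlation. An analysis plan not shown here may already contain the conversion; the protocol text would still need to agree with it.

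**What to change.** Amend Section 8.2 in one of two ways.

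- **Preferred.** In each imputed dataset compute the stratified Mantel-Haenszel risk difference and its standard error (or the signed root of the CMH statistic). Combine by Rubin's rules in PROC MIANALYZE and take the one-sided p-value in the direction of Section 8.8. The risk difference also supplies a pooled estimate and confidence interval.
- **If Wilson-Hilferty is kept.** Add that the one-sided p-value is half the upper-tail p-value of the pooled transformed statistic when the pooled difference favours serlopitant, and one minus that half otherwise. Its exact null rates, 5.3% and 2.6%, run slightly above the nominal 5% and 2.5%.

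Apply the same rule to the Week 4 and 3-point responder tests, and say there whether they are one-sided. The cost is one or two sentences carried into the statistical analysis plan and a few lines of SAS, with no patients and no extra data.

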### **8.3 Analysis Populations**

Primary efficacy analyses will be based upon an intent-to-treat (ITT) philosophy. The primary efficacy population will be the Full Analysis Set (FAS), which will include all randomized subjects who received at least one dose of study drug. Subjects will be analyzed within the treatment group to which they are randomized.

The primary safety population will be all treated subjects with at least one post-baseline assessment. For safety analyses, subjects will be classified based upon the treatment received.

Additional analyses performed on the Per Protocol (PP) population will be considered supportive. The PP population will include all subjects in the safety population who complete the Week 8 evaluations without any significant protocol violations (i.e., any subject or investigator activity that could have possibly interfered with the therapeutic administration of the treatment or the precise evaluation of treatment efficacy). The PP population will include subjects in the safety population who do not meet any of the following criteria:

- Violated the inclusion/exclusion criteria;
- Received a strong CYP3A4 inhibitor (See [Appendix B](#));
- Received an excluded medication which may plausibly impact the primary endpoint at Week 8
- Have not been compliant with the dosing regimen (i.e. subjects must comply with 80–120% of the expected dosage of study medication during participation in the study);
- Have not completed Week 8 visit within  $\pm 7$  days window

Subjects who discontinue from the study drug due to an adverse event related to study treatment or documented lack of treatment effect, or who met protocol-defined non-responder criteria, will be included in the PP population. Prior to breaking the blind, other additional criteria may be added to the lists above to accommodate for unforeseen events that occurred during the conduct of the trial that result in noteworthy study protocol violations.

#### **8.4 Subject Disposition**

An accounting of all randomized subjects by disposition will be presented. Subjects who discontinue study drug prematurely or withdraw from the study will be summarized and listed, with a description of the reason for early termination/withdrawal.

#### **8.5 Subject Characteristics**

Demographic and other baseline characteristics will be summarized.

#### **8.6 Concomitant Medications**

Concomitant medications will be coded by the World Health Organization Drug Dictionary to Anatomical Therapeutic Classification (ATC) and preferred drug name. Concomitant medications will be summarized by ATC level and preferred drug name and listed.

#### **8.7 Treatment Compliance and Extent of Exposure**

Compliance with study drug dosing will be determined based on tablet counts recorded on the eCRF. Compliance will be calculated by analyzing expected number of tablets returned versus actual number of tablets returned. Summaries of treatment exposure will also be produced.

#### **8.8 Efficacy Analyses**

The efficacy endpoints will be summarized within the FAS and PP populations using descriptive statistics by time point and treatment. Results including averaged imputed values will be summarized at Baseline, Week 2, 4, 8 and Follow-up and the change from baseline for these measures will be summarized at Week 2, 4, 8 and Follow-up. The WI-NRS

measures will also be summarized at Week 6. The WI-NRS and change from baseline will also be presented for each study day. The PGIC is a measure of change and so will only be summarized at Week 2, 4, 8 and Follow-up.

For the 4 and 3 point responder rate endpoints, subjects will be considered responders if they have at least a 4 / 3 point reduction between baseline and the corresponding week and the subject did not use an excluded medication to treat their pruritus or psoriasis.

The difference in the primary efficacy outcome measure (WI-NRS 4-point responder rate at Week 8) will be tested using a CMH test controlling for the ‘as randomized’ stratification factors. Conceptually the hypotheses being tested are:

$$H_0: P_{Placebo} \geq P_{Serlopitant} \quad H_a: P_{Placebo} < P_{Serlopitant}$$

where  $P_{Placebo}$  is the percent of placebo responders and  $P_{Serlopitant}$  is the similar percent for serlopitant. The primary endpoint will utilize the missing data rules as outlined in [Section 8.2](#).

The remaining key secondary endpoints will be analyzed using an analysis of covariance (ANCOVA) model with treatment group and stratification factor as fixed effects and the respective baseline values as a covariate. Both least squares means and observed means will be presented.

To confirm the assumptions for the ANCOVA model (i.e., that the errors are normally distributed with equal variances), residuals will be examined using the Shapiro-Wilk test. If there is overwhelmingly strong evidence that the assumptions are not satisfied, the data will be rank-transformed prior to submitting to the ANCOVA. Results of the rank-transformed analysis then will be considered the primary analysis; however, results of the non-rank-transformed analysis will also be presented.

The preceding analyses are to be conducted for the FAS and PP populations.

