## **5.7 Concomitant and Excluded Therapies**

Concomitant therapies include any therapies (including over-the-counter medications) used by a subject from initiation of study drug treatment through the follow-up period. Medications/therapies for which discontinuation was required for the purposes of study participation (i.e., "washout medications/therapies") shall also be documented. A record of all medications used will be maintained for each subject throughout the study. Reported information will include a description of the type of drug, treatment period, dosing regimen, the route of administration, and drug indication.

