### **5.7.2 Excluded Therapies and Study Restrictions**

Therapy exclusions prior to the initial Screening visit are described in [Section 4.3](#). The following therapies and activities are excluded from the initial Screening visit through the follow-up period:

- NK1-R antagonists (other than study drug)
- Systemic biologic therapies, including but not limited to etanercept, infliximab, adalimumab, ustekinumab, secukinumab, or ixekizumab

- Systemic non-biologic psoriasis therapies, including but not limited to systemic corticosteroids, phosphodiesterase-4 inhibitors, Janus kinase inhibitors, cyclosporine, methotrexate, retinoids, hydroxyurea, mycophenolate mofetil, thioguanine, sirolimus, azathioprine, or fumaric acid derivatives
- Topical/local psoriasis therapies other than those permitted per [Section 5.7.1](#), including but not limited to topical corticosteroids, vitamin D analogues, calcineurin inhibitors, phosphodiesterase-4 inhibitors, Janus kinase inhibitors, non-shampoo forms of coal tar, salicylates, retinoids, anthralin, or excimer laser
- Phototherapy, with or without psoralen
- Use of an indoor tanning facility or excessive sun exposure/sunburn
- Systemic therapies with recognized anti-pruritic properties, including but not limited to H1 antihistamines, doxepin, mirtazapine, gabapentin, pregabalin, cannabinoids, and kappa opioid receptor agonists
- Topical anti-pruritic therapies, including but not limited to H1 antihistamines, doxepin, capsaicin, or medicated emollients (e.g., menthol or pramoxine)
- Strong CYP3A4 inhibitors (See [Appendix B](#))
- Any investigational therapy
- Initiation of any bland emollient use after the initial Screening visit

Use of any excluded therapies should be reported to the study medical monitor as soon as possible, and will be recorded as protocol deviations for subjects who receive them.

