### **6.5.9**            *Follow-up Visit*

For all subjects, the Follow-up visit occurs 14 days (+ 3 days) after the Week 8 visit or the last dose of study drug for subjects who discontinue study drug early. Every effort should be made for subjects to complete the Follow-up visit after a subject has discontinued study drug early. At the Follow-up visit, the following procedures and assessments are to be performed:

- Concomitant medications
- Adverse events
- Targeted physical exam
- Vital signs (including weight)
- ECG
- Laboratory
  - Hematology
  - Chemistry
  - Urine pregnancy test for females of childbearing potential (with positive or equivocal results confirmed by a serum pregnancy test)
  - Urinalysis
  - Endocrine
  - Reproductive endocrine labs for females for females under 55 years of age at consent
- BSA
- PGA
- sPGA
- PGIC
- PIQ
- eDiary review
- Study drug compliance (if not previously performed for subjects who discontinued study drug early)
- Collect study drug (if not previously performed for subjects who discontinued study drug early)
- Collect eDiary and actigraphy watches

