## **8.2 Handling of Missing Data and Excluded Therapy Use**

Should a determination of treatment period (on treatment, pre-treatment) be required for adverse events or concomitant medication but the corresponding date is missing, or is a partial date, the event/medication will be considered on treatment unless the portions of the date that are available indicate this is not possible.

The primary method of handling missing efficacy data will be MCMC multiple imputation. Imputation will be conducted within each treatment group independently, so the pattern of missing observations in one treatment group cannot influence missing value estimations in another. For each imputation process, 25 imputations will be performed.

If a subject fails to complete their eDiary for a week or more the primary endpoint (WI-NRS), may be missing. If the Week 8 measure from the eDiary is unavailable because the subject withdrew from the study due to lack of efficacy, or the subject uses an excluded therapy to treat psoriasis or pruritus, their responder status will be defined as non-responder. If the Week 8 value is missing for any other reason, the WI-NRS change from baseline value will be based on imputed data. Missing Week 8 WI-NRS values from which the 4-point responder status is derived will be estimated by MCMC.

Missing WI-NRS data will be derived for the analysis using the method of MCMC multiple imputation. Since both primary and key secondary endpoints require WI-NRS, the following steps will be followed:

1. Using the daily eDiary data, calculate Baseline and Week 2 through Week 8 values by averaging available values. If any values are available, these will be used i.e. a minimum of 1 observation is required to compute a week's average.
2. From step 1, create a dataset for each treatment group, of subjects with observed values and those needing estimation by MCMC. The missing WI-NRS values in each dataset will be filled in using the MCMC method to generate 25 datasets.

The resulting datasets for each treatment arm will be combined into one complete dataset.

Syntax:

```
proc mi data=datain out=dataout seed=&seed. Nimpute=25 <options>;  
  where trtpn=(TRT); /* Note TRT = [1, 2]; depending on treatment group */;  
  mcmc chain=single;  
  var baseline d2 d3 d4 d5 d6 d7 week2 week3 week4 week5 week6 week7 week8;  
run;
```

3. From each complete dataset, the dichotomous responder rate will be determined.

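### Can excluded-medication use after Week 4 or Week 8 overturn an observed response because the responder definition gives it no end date?

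*Protocol*

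**What the plan says.** The responder definition is in section 8.8 and covers both the 4-point and the 3-point rates. A responder has the required reduction from baseline to the "corresponding week and the subject did not use an excluded medication to treat their pruritus or psoriasis".

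Section 8.2 carries a related rule. The sentence opens with a Week 8 diary measure that is unavailable because the subject withdrew for lack of efficacy, and continues "or the subject uses an excluded therapy to treat psoriasis or pruritus, their responder status will be defined as non-responder". The next sentence sends Week 8 values missing for other causes to multiple imputation. There is no Week 4 counterpart.

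The therapies concerned are barred well beyond both assessment weeks. Section 5.7.2 says "The following therapies and activities are excluded from the initial Screening visit through the follow-up period". Section 5.7 defines concomitant therapies as those "used by a subject from initiation of study drug treatment through the follow-up period", so later use will be in the data. Under section 6.5.9, "the Follow-up visit occurs 14 days (+ 3 days) after the Week 8 visit or the last dose of study drug".

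One passage does link excluded use to a time point. Section 8.3 removes from the per-protocol set a subject who "Received an excluded medication which may plausibly impact the primary endpoint at Week 8".

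**The concern.** The rule decides the primary endpoint (4-point response at Week 8), the first key secondary endpoint (4-point response at Week 4) and the 3-point rates at both weeks. Section 8.1 makes testing of the key secondaries "hierarchical with testing starting with the WI-NRS Week 4 responder rate, then the Day 7 WI-NRS endpoint", so the Week 4 result also controls whether Day 7 and Day 3 are tested.

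In 8.8 the named week attaches to the reduction, while the medication condition is a separate clause with no window. One programmer could count use up to the assessed week and another could count any use during the study. Under the second version, events after an assessment would decide its result: about 6 weeks of later use (Weeks 5 to 8 plus 2 weeks of follow-up) for Week 4, and 14 to 17 days for Week 8. Itch treatment after study drug stops is foreseeable, and the direction of any effect would depend on how that use splits between the arms.

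**Working it through.** **1. Where the two readings differ.** Take a subject who has the required reduction at both weeks.

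| First excluded use for itch or psoriasis | Week 4, use to date | Week 4, any use | Week 8, use to date | Week 8, any use |
|---|---|---|---|---|
| By Week 4 | non-responder | non-responder | non-responder | non-responder |
| Weeks 5 to 8 | responder | non-responder | non-responder | non-responder |
| Follow-up only | responder | non-responder | responder | non-responder |

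The readings disagree in three cells: two at Week 4, and at Week 8 only for use confined to follow-up.

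**2. What the text supports.** Each endpoint is a status at a named week. In 8.2, excluded use sits beside withdrawal for lack of efficacy, and the following sentence treats the remaining missing Week 8 values as having other causes. This fits section 5.6, under which receiving an excluded medication for pruritus or psoriasis is a ground for stopping study drug, so that use during treatment can end in no Week 8 value. Use after the Week 8 visit cannot be a reason for lacking that value. Section 8.3 likewise asks whether use could bear on the Week 8 endpoint. These passages point to use up to the assessed week.

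**3. Reproducing the planned power.** Inputs from 8.1: n = 100 per group, 24% v 43.5% at one-sided 5%, 24% v 46% at one-sided 2.5%, chi-squared test. With d the difference, p̄ the mean rate and q = 1 − p:

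power = Φ{[d − z·√(2p̄q̄/n)] / √[(p₁q₁ + p₂q₂)/n]}

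- 43.5%: p̄ = 0.3375, so [0.195 − 1.645 × 0.0669] / 0.0654 = 1.30 and power is 90.3%.
- 46%: p̄ = 0.35, so [0.220 − 1.960 × 0.0675] / 0.0656 = 1.34 and power is 90.9%.

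Both agree with the stated 90%. Counting only use up to the assessed week leaves them unchanged.

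**4. Cost of the literal reading at Week 8.** The protocol gives no rate of follow-up use, so every share below is an assumption. Each responder rate is multiplied by (1 − share).

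| Share of responders overturned | Power, 43.5% scenario | Power, 46% scenario |
|---|---|---|
| None | 90.3% | 90.9% |
| 5% in both arms | 88.2% | 88.6% |
| 10% in both arms | 85.8% | 86.0% |
| 20% in both arms | 80.3% | 79.6% |
| 10%, serlopitant only | 74.8% | 75.0% |
| 10%, placebo only | 95.6% | 96.0% |

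In the first scenario the planning rates imply 24 + 43.5 = 67.5 responders. The 10% row therefore needs about 7 subjects with at least a 4-point improvement to start excluded treatment within 14 to 17 days after Week 8.

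**5. Sensitivity at the decision boundary.** With 100 per arm, z = d / √(2p̄q̄/n):

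- 24 v 37: z = 0.13 / 0.0651 = 2.00, one-sided p = 0.023
- 24 v 36: z = 0.12 / 0.0648 = 1.85, p = 0.032
- 24 v 34: z = 0.10 / 0.0642 = 1.56, p = 0.060
- 23 v 36: z = 0.13 / 0.0645 = 2.02, p = 0.022

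One subject can move a result across 0.025 in either direction. These counts were chosen at the boundary, where one reclassification for any reason does the same, so they say nothing about how likely this one is.

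**6. Week 4.** The readings differ most here, but the protocol gives neither a Week 4 planning rate nor a rate of later use. No effect can be calculated.

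**The case for a change.** The strongest case for a change is that the protocol did not leave this rule to the SAP. It wrote the medication condition into the endpoint and omitted the window. Section 8.2 can also be parsed so that excluded use is a free-standing condition unconnected with a missing value, and 8.8 plainly applies the condition to subjects whose score was observed. The per-protocol wording in 8.3 does not govern response. A one-clause clarification would cost almost nothing, since therapy periods are already recorded.

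Much of this is right. No sentence states the end date, and the start is unstated too, so use during screening would also count on a strict reading. For Week 4, 8.2 offers no help.

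It does not follow that the plan defines the endpoint wrongly. The literal reading makes a week-specific status depend on what happens after that week, which few analysts would program without asking. Nor is there a conflict with 8.3: that section expressly keeps subjects who meet non-responder criteria in the per-protocol set, so membership and response status are separate matters. The protocol also leaves open which diary days make up each analysis week, and a medication cut-off at the end of an analysis week depends on those days. The two belong together in the SAP.

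**Conclusion.** The clause in 8.8 is undated, but this is a gap that analysts fill sensibly. The natural window is use up to the assessed week. For Week 8, section 8.2 already points that way; for Week 4, the meaning of a status at a named week supplies it. Section 8 requires the SAP to be final before unblinding, so the window can be fixed without knowledge of results.

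No effect on power or on the decision rule has been established. The fall from about 90% to about 86% rests on an assumed 10% reclassification in both arms, and the one-arm figures are stress cases. The real ambiguity is at Week 4, a key secondary endpoint tested only if the primary succeeds, and its size cannot be computed from the protocol. This conclusion assumes that the SAP, which is not at hand, states the window when it defines the analysis weeks and says how use during screening is treated.
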